Study personnel will have access to patients' electronic medical records for screening, eligibility confirmation purposes. Study personnel will also have access to patients past medical history and demographic data. The information used for screening or enrollment purposes and study analysis. This data will be extracted using Clarity. On the servers that host the Facebook language-extraction application, we will not collect identifiable information. Instead, we will use the Facebook/Instagram mechanism to generate a unique random ID. This ID will be used to track users and will be stored together with their survey results on the client-facing server. If disclosed, the unique random ID cannot be traced back to a given individual (unlike the Facebook/Instagram user ids, which can comparatively simply be resolved into identifiable information). In addition to this user-facing server (application server), we will also have a Secure Data Repository, which will receive the Facebook user id from the application server and will then proceed to query the Facebook/Instagram Application Programming Interface (API) for (identifiable) user information and Facebook/Instagram statuses the users have written on Facebook/Instagram. This we can only do once the user has joined our application, these privileges are managed through Facebook's/Instagram's systems of access tokens. The Secure and the Application server would use the same access token, but only the Secure Server would pull identifiable user information, whereas only the Application server would interact directly with the users (and is thus more at risk for code injection and other hacking attacks). The secure data repository will be housed on servers under our control at the University of Pennsylvania, such that no data we collect will be stored out of our control. All language data will be stored on the Health Service Research Data Center (HSRDC). As per the HSRDC Data Management Policy and Procedures Manual, password protection is used at the server and web portal levels for all transactions that allow entry and editing of data, or provide access to sensitive subject data or administrative privileges. Passwords will be managed to require all users to change their password within 90 days and strict rules will be implemented to require strong passwords. Additionally, all PHI data will be encrypted and linked to survey data through a study ID number, with linkage and de-encryption keys activated only by a user password for which a member of the research team has been given permission to access these sensitive data (Principal Investigator [name] and project staff who are under the direct supervision of the PI). As per the HSRDC Data Management Policy and Procedures Manual, the database management on these servers is built with multiple layers of security and follows best practices for securing sensitive data. The main levels of security are fourfold and include machine physical security at the IT facility at which the servers are housed, physical server security in the highly restricted server containment room, electronic server security (firewalls, passwords, encryption) restricting access to the machine, and directory access controls restricting access to these particular data. We will consult the PI, ED physician to manage participant safety concerns and serve as the clinical contact point person. The data security of the applications is as follows: Facebooks General Data Protection Regulation - <https://www.facebook.com/business/gdpr> Instagram Data privacy webpage, <https://help.instagram.com/519522125107875> Google

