2. Is this a multi-center study where the Penn IRB will be asked to serve as the IRB of Record for other external study sites?

No

Other Sites

No other sites

Protocol

Abstract

Cardiovascular disease is the leading cause of death in the US. While prevention approaches have improved longevity of patients, risk factors and adverse health behaviors (e.g., physical inactivity, smoking) are highly prevalent. The logistics and practicalities of meeting the goal of ideal CV health have not been clearly elucidated. Practice guidelines recommend using the Framingham risk score (FRS) or other risk prediction tools to classify patients risk of CV disease. These models however are imprecise and there is increasing focus on identifying markers that provide better measures of risk. As digital platforms are increasingly used to document lifestyle and health behaviors, data from digital sources may provide a window into manifestations of novel risk factors and potentially a better characterization of existing risk factors.

Objectives

Overall objectives

This study has three main objectives. (1) Identify and characterize topics and features derived from digital data (e.g., social media, online search, mobile media) which are associated with CHD and related risk factors and develop phenotypes of how patients use and engage with social media and then determine the association of these phenotypes with health status, social media perceptions, and patient activation. (2) Quantify and validate the incremental benefit of adding variables from patients' digital data to conventionally-derived predictive models of CHD (e.g. Framingham risk score/American College of Cardiology ASCVD Risk Estimator Plus) using a retrospective cohort of patients with and without heart disease. (3) In a cohort of patients with and without heart disease, develop and evaluate models that use digital media data to predict health care utilization (e.g. cost). (4) Evaluate the impact of dynamic health events (e.g. COVID-19) on modifiable CV health behaviors (smoking, diet, activity) using population level-digital media data (e.g. Facebook, Twitter)

Primary outcome variable(s)

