The primary outcome variable for the first objective will be topics and features (derived using the Latent Dirichlet Allocation [LDA] method for clustering language data) as well as a model-based approach of latent class analysis (LCA). We hypothesize: H1: There will be a difference in themes and topics posted by patients with heart disease and for patients without heart disease and use and engagement

phenotypes reflecting quantity, quality, and interaction of posts will be associated with health status, social media perceptions, and patient activation. The second objective outcome variable will be any CHD event. We hypothesize: H2: Adding digital data variables to conventionally-derived predictive models will improve the AUC for forecasting/predicting a CHD related event in a patient. The third objective outcome measure will be health care utilization measured by cost. We hypothesize: H3: Unique digital data variables identified for patients with heart disease and without heart disease will better predict future health care utilization costs for the health system. The fourth objective outcome measure will be the impact of dynamic health events on CV health behaviors. We have the following three hypotheses: H4,1: Digital media data will provide valid measures of health behaviors when compared with traditional sources. H4,2: Variations in digital data about modifiable CV health behaviors will correlate with dynamic health events. H4,3: Modifiable CV health behaviors (smoking, poor diet, and reduced physical activity) will increase more in response to dynamic health events in low income and minority communities.

Secondary outcome variable(s)

Given the correlational nature of this research the distinction between primary and secondary outcome variables is not particularly apparent.

Background

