
Study Design

Phase*

Not applicable

Design

We will identify patients ages 30-74 with and without CVD) within the last 5 years who receive care through the University of Pennsylvania Health System or receive care in another health system in the United States (U.S.). For patients with CVD, we will be using the following ICD codes for identification: ICD 10: I63, I20-I25. For patients without CVD, please find attached the list of ICD 10 codes we will use for identification. UPHS is the largest health system in Eastern Pennsylvania with a diverse patient population of more than 500,000 patients with CV disease. We will recruit both in and out-patients as study participants. For both the inpatient population and outpatient population within

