UPHS, we will use Epic workbench and other Epic screening tools such as the Best Practice Alerts (BPA) to screen for eligible patients. BPAs can be configured to identify patients given a set of inclusion criteria, in real-time, and send a silent in-basket message to allocated study personnel. Users gain access to these alerts through an in-basket message pool within PennChart, BPA distribution and modification privileges can be controlled (and limited) based on security configurations. Penn Medicine sites identified in the BPA include PCAM, HUP, PPMC, PAH, CCH, Cardiology HVC Consultative Clinic, Cardiology HVC Clinic, PCAM, Cooper/PIMA Internal Med, Penn Cardiology Bucks County, Penn Cardiology South Philly, Penn Cardiology Valley Forge, Penn Medicine Bala Cynwyd, Penn Heart and Vascular Center Washington Square, Penn Cedar and Penn Heart and Vascular Center Radnor, PA. For patients who are identified outside of UPHS, we will solely rely on self-report diagnosis for identification. Potentially eligible patients will either be approached or emailed/called about the opportunity to participate in the study either in person during an in-patient visit (4,734,948/annually) or outpatient visit at Penn Medicine hospital, including the Emergency Rooms at the Hospital of the University of Pennsylvania (HUP), Penn Presbyterian Medical Center, and Pennsylvania Hospital, or at one of the Outpatient Internal Medicine Clinics in Philadelphia, or contacted remotely (over a secure calling phone application or emailed). Additionally, we will contact patients remotely at various Penn Medicine Chester County locations such as Lancaster General and Chester County hospital. For initial interest participation emails and follow-up emails, we will be using a shared Penn Medicine email account through our Center ([contact]) to reach out to those folks. In addition to emailing and calling patients, we will be using My Penn Medicine (MPM) which is UPHS's secure patient portal to message identified patients about interest in our study. Our message will use the same template as our initial outreach email. Another form of remote outreach we will be using is Way to Health (W2H), which is a HIPAA secure two-way texting platform, where we will text message identified patients our initial outreach message about our study (reference the text message automated flow attached). If patients are interested, they will be texted our eligibility survey link to complete. We will also use this HIPAA secure text messaging platform to follow up with participants related to various study participation (i.e. re-sharing of data through a secure link, scheduling confirmation). Interested participants who are eligible will be asked to fill out a short survey asking what days and times work best for a team member to give them a call to walk through what is involved in participating in the study. We will use the Academic Associate (AA) Program in the Emergency Department (ED) at the Hospital of the University of Pennsylvania, Presbyterian Medical Center to identify patients. The AA Program provides premedical and pre-health post-baccalaureate students an opportunity to engage in clinical and translational research activities. The AAs have Immunization records (measles, mumps, and rubella [MMR] and varicella [chickenpox]) and TB screening (PPD test or equivalent), and influenza (in season) and complete a web-based course sponsored by the University of Pennsylvania on the protection of human subjects in research. Using Epic tools and AAs, we will screen all patients aged 30-74 examining their chief complaint recorded in Epic. If patients present cardiovascular-related chief complaints, the patient will be noted in a screening log, and if admitted, note their in-patient ICD-10 admission code. Similarly, for patients aged 30-74 who have a non-cardiovascular-related chief complaint, the patient will be noted in a screening log and if admitted, note their in-patient ICD-10 admission code. For in-person recruitment and enrollment in the outpatient setting, outpatient Penn Medicine clinics (e.g. Internal Medicine, Primary Care, Cardiology), RAs will review the weekly appointment list to review if any patients meet either case and control requirements. RAs will be in communication regularly with the nursing coordinator, office manager, charge nurse, nurse/ physician team to determine the daily census and appropriateness of approaching patients. In both in and outpatient settings, the AAs or CDH research staff will approach and will introduce the study in brief and if the patient is interested in enrolling. They query eligible patients about their interest in study enrollment (i.e. sharing their social media, online search, or step tracking data and allowing access to their EMR data and health insurance data). For remote recruitment and enrollment, identified patients via the BPA and EPIC reporting workbench will either be emailed, called, sent an MPM message, or a W2H message in regards to interest in participating in this research study. Initial interest participation emails and all follow-up emails will be sent using our Centers shared Penn Medicine email account ([contact]), MPM messaging, or W2H messaging. All recruitment and follow-up emails will be A/B tested, also known as split testing, the process of comparing two identical versions of an email. Potential variations include the order of information, email headers, and signatures. NOTE: In addition to the research team reaching out to potentially eligible patients, we will be using flyers, we will post our study on Penn Medicine Lancaster General Health's various social media sites (i.e. Facebook, Instagram, Twitter, LinkedIn, etc.), and we will be posting our study on iConnect for interested patients to reach out to us regarding participation in the research study. We will be using iConnects pre-screener feature to assess patients for pre-eligibility for our study. These pre-

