We will identify patients ages 30-74 with and without CVD) who receive care in the University of Pennsylvania Health System or in another health system in the United States (U.S.). For patients with CVD, we will be using the following ICD codes for identification :ICD 10: I63, I20-I25. For patients without CVD, please find attached the list of ICD 10 codes we will use for identification

Subjects enrolled by Penn Researchers

1000

Subjects enrolled by Collaborating Researchers

0

Accrual

Patients will be contacted via email/phone call to participate in the study or in person during an inpatient admission from the Emergency Department at HUP, PAH, or PPMC or an out-patient visit at Penn Medicine Primary care clinics, Internal Medicine, Cardiology clinics or if they are a patient in another health system, we will reach out to them via email or phone call

Key inclusion criteria

- 30-74 years of age - Willing to sign informed consent - Primarily English speaking (for language analysis)
- Has an account on any of the following digital data platforms (Facebook, Instagram, Twitter, Reddit, Google (gmail), or smartphone or wearable device such as Apple Health, Fitbit, Samsung Health, MapMyFitness or Garmin) and willing to share data
- If has social media account, Instagram or Facebook, willing to share historical and prospective data (60 days)
- If has Google (gmail) account, willing to download and share google takeout zip file
- If has smartphone or wearable device, willing to share step data
- Willing to share access to medical health records
- Willing to share healthcare insurance information

For the Objective 1 subgroup:

- 30-74 years of age
- Willing to sign informed

consent Willing to complete an online survey

Key exclusion criteria

- Patient does not meet age inclusion criteria above - Does not use and post on digital data sources we are studying or unwilling to donate data
- Patient is in severe distress, e.g. respiratory, physical, or emotional distress
- Patient is intoxicated, unconscious, or unable to appropriately respond to questions
- Patient has a history of heart attack, stroke, or CAD more than 5 years ago. For the Objective 1 subgroup:
 - Not between 30-74 years of age
 - Unwilling to sign informed consent
 - Unwilling to complete an online survey

Vulnerable Populations

Children Form

Pregnant women (if the study procedures may affect the condition of the pregnant woman or fetus) Form

Fetuses and/or Neonates Form

Prisoners Form

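### Objective 2 states no index date, Cox time origin or predictor cut-off, so a higher AUC would not by itself show that digital data forecast CHD rather than recognise it

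*Protocol*

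**What the plan says.** **The claim.** Under Primary outcome variable(s), the Protocol states "H2: Adding digital data variables to conventionally-derived predictive models will improve the AUC for forecasting/predicting a CHD related event in a patient". The outcome is given in one sentence: "The second objective outcome variable will be any CHD event". It is not described as first, recurrent or already present, and no prediction horizon is given.

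**The cohort.** Overall objectives describes Objective 2 as "using a retrospective cohort of patients with and without heart disease". Study Design: Design says "We will identify patients ages 30-74 with and without CVD) within the last 5 years", and for cases "For patients with CVD, we will be using the following ICD codes for identification: ICD 10: I63, I20-I25". For people outside the health system, "we will solely rely on self-report diagnosis for identification". Key exclusion criteria removes only older disease: "Patient has a history of heart attack, stroke, or CAD more than 5 years ago".

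**The digital windows.** Key inclusion criteria asks Facebook and Instagram users to be "willing to share historical and prospective data (60 days" forward). Study Design: Design adds that Google data look back from the download, Garmin gives monthly steps for the past 12 months, and S Health gives daily steps for the 34 days before export. All of these are anchored to enrolment or export.

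**The analysis.** For Objective 2, the Protocol Analysis Plan and the SAP carry the same text: a weighted Cox model for each digital variable, a check of proportional hazards, and four models built from Framingham/ASCVD inputs with or without SES and digital features. Neither gives an index date, a time origin, a risk set or a date limit on predictors. AUC is not mentioned in that text.

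**The concern.** Forecasting requires every predictor to precede the event. Here cases are selected on disease already present, while the data windows end at or after enrolment. For a case diagnosed before enrolment, the whole 60-day feed follows the qualifying diagnosis. The planned text classifiers include symptoms, treatment and medication adherence, and such content can arise because the disease is already known.

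A higher AUC could then come partly from the model recognising people who have CHD. The plan as written gives no means of telling this apart from real forecasting value, and the choice of data window would be left to the analyst after the data are in hand. The Cox model also has no clock: without a time origin and a risk set, its hazard ratios have no defined meaning.

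**Working it through.** **1. Two readings of the outcome.**
- *The qualifying diagnosis is the event.* The retrospective cohort and the five-year case window are compatible with this. Post-diagnosis data may then enter. The documents do not say that they will, but no rule keeps them out.
- *Events after enrolment are counted.* A Cox model is planned, and insurance and cost information is collected for up to five years, direction unstated. Data from before enrolment are then proper predictors, but the start of follow-up and the people at risk are undefined.

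**2. Size under the first reading.** The documents give no AUC, event count or event timing for Objective 2, so there is no figure of theirs to reproduce. The inputs below are assumptions, except the collection windows.
- H = 5 or 10 years of evenly spaced Facebook/Instagram history, plus the Protocol's 60 days (60/365.25 = 0.164 year).
- t = years from event to enrolment, uniform from 0 to T.
- Base AUC 0.70 to 0.80; a digital score, independent of the base score, with no pre-event signal and a shift of d = 0.2 to 1.0 SD after the event.

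Post-event share of posts: f = mean of (t + 0.164)/(H + 0.164). For T = 5 and H = 5 this is (2.5 + 0.164)/5.164 = 0.516.

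AUC gain (binormal): d0 = √2 × Φ⁻¹(AUC0); gain = Φ(√(d0² + (f·d)²)/√2) − AUC0. For AUC0 = 0.70, d0² = 0.550. With f·d = 0.516, the new AUC is Φ(√(0.550 + 0.266)/√2) = 0.7385, a gain of 0.0385.

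| Case timing | Post-event share f (H = 10 to H = 5) | False AUC gain |
|---|---|---|
| Enrolled at index admission (T = 0) | 0.016 to 0.032 | at most +0.0002 |
| Uniform over 1 year | 0.065 to 0.129 | at most +0.0027 |
| Uniform over 5 years | 0.262 to 0.516 | +0.0002 to +0.039 |
| All data post-event | 1 | +0.003 to +0.11 |

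A simulation in which f varies between cases (H = 5, T = 5, d = 1, base 0.70) gave 0.037 against 0.0385. The last row applies only to the 60-day feeds used alone, or to step windows lying wholly after the event.

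**3. Step windows.** The share of cases whose window W lies wholly after the event is 1 − min(1, W/T). Uniform over five years: S Health 1 − 34/1826.25 = 98%, Garmin 1 − 1/5 = 80%. Uniform over one year: 91% and 0%. At the index admission: almost none for either.

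**The case against.** A retrospective cohort, a forecasting hypothesis and Cox models together suggest a familiar design: dated historical exposure followed forward to an event already in the record. On that view the ICD codes and the five-year window are recruitment rules, and nothing makes the qualifying diagnosis the Objective 2 outcome. This is a fair reading. It still needs a time origin and a date limit on exposure, and neither is stated.

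The Protocol also calls the research correlational. That remark explains why primary and secondary outcomes are not separated; the same section still states a forecasting hypothesis.

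The size rests on assumed inputs and is negligible for enrolment at the index admission, which is a named recruitment route. This stands, and it limits the severity. In the other direction, the calculation spreads the shift evenly over posts, so a single explicit mention of a past heart attack could count for more than it allows.

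Garmin and S Health have the shortest stated look-backs. Apple Health, Fitbit, Google Fit and MapMyFitness have no stated short limit, so the step figures do not describe all step data.

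The Design section cites a data collection manual that was not available here. It is described as covering extraction. If it contains a window rule, the analysis text should state it.

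**Conclusion.** The omission is established in both documents and should be fixed before analysis. As written, an AUC gain in Objective 2 does not by itself support the forecasting claim in H2. Under one reading, post-diagnosis data can contribute to the gain; under the other, follow-up and the risk set are undefined.

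The illustrated bias runs from about zero to +0.04 for social media history, and to +0.11 only where everything used is post-event. These figures depend on the assumed event timing, shift, base AUC and posting history. They show that a false gain is possible, not how large it would be in this study.

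A reader might infer that any gain would be spurious, or that the result could never be reported as forecasting. The documents do not support either. They do not say that post-event data will be used, they collect historical data that could support a pre-event analysis, and what may be reported depends on the data actually used.

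**What to change.** In the Objective 2 text of both Protocol and SAP, choose one of two options.

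**(a) Keep forecasting.**
- State which event is the outcome, an index date for cases and for controls, and the Cox time origin and risk set.
- Restrict all predictors (digital, Framingham/ASCVD and SES) to values dated before the index date, with one stated lead-time gap and a sensitivity analysis on it.
- Exclude the 60-day feeds and step windows whenever they fall after the index date.
- For undated fields (follower counts, profile snapshots, SES surveyed at enrolment), either state the assumption that they are stable or leave them out of the forecasting comparison.
- Report any model using post-event data as classification of existing CHD.
- State as a limitation that retrospective cases had to survive to enrol, which a date filter does not correct.

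**(b) Reword H2** as discrimination of existing CHD and drop the forecasting conclusion.

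**Cost.** Option (b) is wording only. Option (a) needs plan text and a date filter. The Design section lists times or dates for Twitter, Instagram and Google, and Subject Confidentiality gives access to past medical history. Facebook time stamps are not listed and need confirming.

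With events uniform over five years, the share of a case's posts kept is the mean of max(0, H − t − gap)/(H + 0.164): 48–74% with no gap and 44–71% at 90 days. At the index admission it is 97–98% and 92–96%. Garmin data are monthly totals, so the index month must be left out. Usable cases are then (11/12 year − gap)/5 years: 18% with no gap and 13% at 90 days. S Health is usable for at most 34/1826.25 = 1.9%. Some participants outside the health system with undated diagnoses would be lost, and the AUC gain would probably be smaller.
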